9.5.2 Local Disease-Free Survival

Defined as the duration of time from surgical resection of the primary tumor until local recurrence or death, whichever occurs first.

9.5.3 Distant Disease-Free Survival

Defined as the duration of time from registration until development of distant metastatic disease or death, whichever occurs first. Subjects with stage IV disease will be censored from this analysis.

9.5.4 Disease-Free Survival

Defined as the duration of time from surgical resection to local recurrence, distant metastatic disease, or death, whichever occurs first. Subjects with stage IV disease will be censored from this analysis.

9.5.5 Progression-Free Survival

Defined as the duration of time from registration to progressive disease (per RECIST), local recurrence, distant metastatic disease (exclusive of stage IV subjects), or death, whichever occurs first.

9.5.6 Overall Survival

Defined as the interval of time from registration until death from any cause.

10. ETHICAL AND REGULATORY REQUIREMENTS

10.1 Protocol Review

The protocol and informed consent form for this study must be reviewed and approved in writing by the OHSU Knight Cancer Institute (CI) Clinical Research Review Committee (CRRC) and appropriate Institutional Review Board (IRB) prior to any patient being registered on this study.

10.2 Informed Consent

Written informed consent will be obtained from all patients, or the legally authorized representative of the patient, participating in this trial, as stated in the Informed Consent section of the case of Federal Regulations, Title 21, Part 50. If a patient's signature cannot be obtained, and for all patients under the age of 18, the investigator must ensure that the informed consent is signed by the patient's legally authorized representative. Documentation of the consent process and a copy of the signed consent shall be maintained in the patient's medical record.

10.3 Changes to Protocol

Any modification of this protocol must be documented in the form of a protocol revision or amendment signed by the principal investigator and approved by the CRRC and IRB, before the revision or amendment may be implemented. The only circumstance in which the amendment may be initiated without regulatory approval is for a change necessary to eliminate an apparent and immediate hazard to the patient. In that event, the investigator must notify the CRRC and IRB in writing within 10 working days after the implementation. Investigators holding the IND must notify FDA of substantive changes to the protocol.

10.4 Maintenance of Records

If the investigator relocates or for any reason withdraws from the study, the study records must be transferred to an agreed upon designee, such as another institution, another investigator, or to OHSU Knight Cancer Institute Clinical Research Management. Records must be maintained according to sponsor or FDA requirements.

10.5 OHSU IRB Reporting of Unanticipated Problems and Adverse Events

Unanticipated Problems (UP) and Adverse Events (AE) will be reported to IRB according to the policies, procedures and guidelines posted on the OHSU IRB web site <http://www.ohsu.edu/research/rda/irb/policies.shtml>.

Fatal and life-threatening UP will be reported to OHSU IRB within 7 days of notification of the event. All other UP reports will be submitted to OHSU IRB no later than 15 days of occurrence or notification of the event. Copies of the report documents will be kept in the study regulatory binder. If any of these require a change (as determined by the PI or the IRB) to the protocol or consent form, the PI will make those changes promptly and submit the revised documents to the OHSU IRB.

UP and AE reports are submitted through OHSU e-IRB and will be reviewed by OHSU Knight Cancer Institute and IRB. Monthly accumulative reports will be reviewed by a DSMC Oncologist and forwarded to the CRRC.

10.6 Adverse Event Definitions

10.6.1 Adverse Event

An adverse event is any untoward medical occurrence in a subject or clinical investigation subject administered with a pharmaceutical product. The adverse event does not necessarily have to have a causal relationship with this treatment. An adverse event can therefore be any unfavorable and unintended sign (including an abnormal laboratory finding), symptom, or disease temporally associated with the use of an investigational product, whether or not considered related to the medicinal product.

Adverse events associated with the use of a drug in humans, whether or not considered drug related, include the following:

- An adverse event occurring in the course of the use of a drug product in professional practice.
- An adverse event occurring from an overdose whether accidental or intentional.
- An adverse event occurring from drug abuse.
- An adverse event occurring from drug withdrawal.
- An adverse event where there is a reasonable possibility that the event occurred purely as a result of the subject's participation in the study (e.g. adverse event or serious adverse event due to discontinuation of anti-hypertensive drugs during wash-out phase) must also be reported as an adverse event even if it is not related to the investigational product.

The clinical manifestation of any failure of expected pharmacological action is not recorded as an adverse event as it is already reflected as a data point

captured in the CRF. If, however, the event fulfills any of the criteria for a “serious” adverse event, it must be recorded and reported as such.

10.6.2 Serious Adverse Event

A serious adverse event is any untoward medical occurrence that at any dose:

- Results in death.
- Is life-threatening.
- Requires in-patient hospitalization or prolongation of existing hospitalization.
- Results in persistent or significant disability or incapacity.
- Is a congenital anomaly or birth defect.
- Is an important medical event.

Life-threatening: The term “life-threatening” in the definition of “serious” refers to an adverse event in which the subject was at risk of death at the time of the event. It does not refer to an adverse event which hypothetically might have caused death if it were more severe.

Hospitalization: Any adverse event leading to hospitalization or prolongation of hospitalization will be considered as Serious, UNLESS at least one of the following exceptions is met:

- The admission results in a hospital stay of less than 12 hours.

OR

- The admission is pre-planned (i.e., elective or scheduled surgery arranged prior to the start of the study).

OR

- The admission is not associated with an adverse event (e.g., social hospitalization for purposes of respite care).

However it should be noted that invasive treatment during any hospitalization may fulfil the criteria of ‘medically important’ and as such may be reportable as a serious adverse event dependant on clinical judgement. In addition where local regulatory authorities specifically require a more stringent definition, the local regulation takes precedent.

Disability means a substantial disruption of a person’s ability to conduct normal life’s functions.

Important medical event: Any adverse event may be considered serious because it may jeopardize the subject and may require intervention to prevent another serious condition. As guidance for determination of important medical events refer to the “WHO Adverse Reaction Terminology – Critical Terms List. These terms either refer to or might be indicative of a serious disease state. Such reported events warrant special attention because of their possible association with a serious disease state and may lead to more decisive action than reports on other terms.

10.6.3 Unexpected Adverse Event

An unexpected adverse event is any adverse drug event, the specificity or severity of which is not consistent with the current Package Inserts for Nexavar (sorafenib). Also, reports which add significant information on specificity or severity of a known, already documented adverse event constitute unexpected adverse events. An event more specific or more severe than described in the package insert would be considered “unexpected”.

10.6.4 Relationship of Adverse Event to Investigational Product

The assessment of the relationship of an adverse event to the administration of study drug is a clinical decision based on all available information at the time of the completion of the case report form.

An assessment of ‘No’ would include:

- The existence of a clear alternative explanation, e.g. mechanical bleeding at surgical site.

OR

- Non-Plausibility, e.g. the subject is struck by an automobile when there is no indication that the drug caused disorientation that may have caused the event; cancer developing a few days after the first drug administration.

An assessment of ‘Yes’ indicates that there is a reasonable suspicion that the adverse event is associated with the use of the investigational drug.

Factors to be considered in assessing the relationship of the adverse event to study drug include:

- The temporal sequence from drug administration: The event should occur after the drug is given. The length of time from drug exposure to event should be evaluated in the clinical context of the event.
- Recovery on discontinuation (de-challenge), recurrence on reintroduction (re-challenge): Subject’s response after drug discontinuation (de-challenge) or subjects response after drug re-introduction (re-challenge) should be considered in the view of the usual clinical course of the event in question.
- Underlying, concomitant, intercurrent diseases: Each report should be evaluated in the context of the natural history and course of the disease being treated and any other disease the subject may have.
- Concomitant medication or treatment: The other drugs the subject is taking or the treatment the subject receives should be examined to determine whether any of them may be suspected to cause the event in question.
- The pharmacology and pharmacokinetics of the test drug: The pharmacokinetic properties (absorption, distribution, metabolism and excretion) of the test drug(s), coupled with the individual subject’s pharmacodynamics should be considered.

10.6.5 Intensity (Severity) of the Adverse Event

The intensity or severity of adverse events should be graded according to NCI-CTC version 4.0 criteria.

10.6.6 Adverse Event Documentation

All adverse events occurring after the subject has signed the informed consent must be fully recorded in the subject's case record form.

Documentation must be supported by an entry in the subject's file. A laboratory test abnormality considered clinically relevant, e.g., causing the subject to withdraw from the study, requiring treatment or causing apparent clinical manifestations, or judged relevant by the investigator, should be reported as an adverse event. Each event should be described in detail along with start and stop dates, severity, relationship to investigational product, action taken and outcome.

10.7 Reporting of Serious Adverse Events to the Sponsor

Each serious adverse event must be followed up until resolution or stabilization, by submission of updated reports to the designated person. An isolated laboratory abnormality that is assigned grade 4, according to CTC definition, is not reportable as an SAE, unless the investigator assesses that the event meets standard ICH criteria for an SAE. CTC grade 4 baseline laboratory abnormalities that are part of the disease profile should not be reported as an SAE, specifically when they are allowed or not excluded by the protocol inclusion/exclusion criteria.

When required, and according to local law and regulations, serious adverse events must be reported to the Ethics Committee and Regulatory Authorities.

All serious adverse events should be reported to Bayer/Onyx within 24 hours. In the event of such an event, the investigator should refer to the Pharmacovigilance section of the contract for reporting procedures. In brief:

The Investigator/Sponsor may report serious adverse drug reactions (SADRs) using either:

An ADEERS form (Adverse Event Expedited Reporting System) available at <http://ctep.cancer.gov/reporting/adeers.html>

OR

A MedWatch form available at <http://www.fda.gov/medwatch/>

All reports shall be sent electronically to:

Electronic Mailbox: [contact]

[contact]

Address: Global Pharmacovigilance - USA

Mail only Bayer HealthCare Pharmaceuticals Inc.
[name]
[name]

Address: [name]

FDX or UPS only [name]

Reports for all Bayer products can also be phoned in via our Clinical Communications Dept:

[contact]

10.8 OHSU Knight Cancer Institute Data and Safety Monitoring Plan

In addition to complete study and pharmacy files, complete records must be maintained on each patient treated on this protocol. OHSU Knight Cancer Institute (CI), through the auditing function of the Knight Clinical Trials Office, is responsible for ensuring that all member investigators and affiliate investigators conduct clinical research studies in compliance with local IRB standards, FDA regulations and NIH policies. The Data and Safety Monitoring Committee (DSMC) is responsible for conducting Quality Assurance audits on CI approved protocols according to the Data and Safety Monitoring Plan policies and procedures

<http://ozone.ohsu.edu/cancer/sharedres/kctoresdocs.cfm>

Locally initiated studies will be audited by an OHSU Knight CI Auditor. Newly approved studies may be audited any time after enrollment has been initiated. Each OHSU Knight approved treatment protocol will be audited on an annual basis in accordance with the Knight Data and Safety Monitoring Plan. .

10.9 Inclusion of Women, Minorities and Children

10.9.1 Inclusion of Women and Minorities

No OHSU Knight Cancer Institute study will focus on any particular gender, racial or ethnic subset. No subject will be excluded from the study on the basis of gender, racial or ethnic origin. Male, female and minority volunteers will be recruited for this study from the general population and approximately 50% men and 50% women will be studied.

Table 1: Population Demographics - Oregon (%)

Ethnic Category	Sex/Gender		
	Females	Males	Total
Hispanic or Latino			11.7
Not Hispanic or Latino			88.3
Ethnic Category: Total of all subjects*			100*
Racial Category			
American Indian or Alaskan Native			1.4
Asian			3.7
Black or African American			1.8
Native Hawaiian or other Pacific Islander			0.3
White			83.6

Ethnic Category	Sex/Gender		
	Females	Males	Total
More than one race			3.8
Unknown/Other			5.3
Racial Category: Total of all subjects*			100*
TOTALS	50.4	49.6	100*

Source: Adapted from U.S. Census Bureau, 2000 *Totals may not equal 100 due to rounding

Table 2: Projected Accrual for the Present Study (enter actual estimates, not percentages).

Ethnic Category	Sex/Gender			
	Females	Males	Unknown	Total
Hispanic or Latino	1-2	1-2	0	2-3
Not Hispanic or Latino	8-9	8-9	0	17-18
Unknown	0	0	0	0
Ethnic Category: Total of all subjects	10	10	0	20
Racial Category				
American Indian or Alaskan Native	0-1	0-1	0	0-1
Asian	0-1	0-1	0	0-1
Black or African American	0-1	0-1	0	0-1
Native Hawaiian or other Pacific Islander	0-1	0-1	0	0-1
White	8-9	8-9	0	16-17
More than one race	0-1	0-1	0	0-1
Unknown	0-1	0-1	0	0-1
Racial Category: Total of all subjects	10	10	0	20

Source: Adapted from U.S. Census Bureau, 2010.

10.9.2 Inclusion of Children

In accordance with NIH guidelines on the inclusion of children as participants in research involving human subjects, children under the age of 18 years must be included in all human subjects' research, conducted or supported by the NIH, unless there are clear and compelling reasons not to include them. Therefore, proposals for research involving human subjects must include a description of plans for the inclusion of children.

This protocol does not include children <18 years of age for the following reason: no dosing or adverse event data are currently available on the use of sorafenib in combination with ifosfamide and epirubicin in children, therefore,

children <18 years of age are excluded from this study but will be eligible for future pediatric phase 2 combination trials.

11. STATISTICAL CONSIDERATIONS

This is a single-stage, single-arm phase II clinical trial to determine the pathologic response rate ($\geq 95\%$ necrosis) in the operative specimen.

11.1 Study endpoints

11.1.1 Primary endpoint

The primary endpoint is the pathologic response rate.

11.1.2 Secondary endpoint

Secondary endpoints include level of toxicity, wound complication rate, overall survival, overall disease-free survival, distant disease-free survival and local disease-free survival.

11.2 Statistical analysis plan

Descriptive statistical analysis will be conducted for the primary and secondary endpoints. The proportion with 95% confidence interval will be summarized for the categorical variables. Method of Kaplan-Meier will be used to estimate the survival functions.

We will also conduct exploratory analysis to investigate levels of tumor proliferation and angiogenic markers including p-ERK, VEGF, sVEGFR-2, bFGF in the plasma and tumor tissue at baseline, during, and after treatment with sorafenib plus chemoradiotherapy and to evaluate expression of tumorigenic and angiogenic factors including p-ERK, VEGF-R2 and PDGFR in tumor tissue by immunohistochemical staining. These analyses will be conducted in an exploratory manner with the aim of generating clinically and biologically interesting hypotheses.

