11.3 Sample size consideration

This is a single-stage single-arm phase II clinical study. We expect to enroll a total of 20 patient for achieving 80% power at a significance level of 5% using one-sided binomial test. The null hypothesis to be tested is that the pathologic response rate is 25%, and we assume the pathologic response rate after preoperative treatment with sorafenib, epirubicin, ifosfamide and hypofractionated radiation for high risk soft tissue sarcomas is at least 52%.

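### Does the descriptive 95% interval in section 11.2 undercut the one-sided 5% test that sizes the trial?

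*Combined protocol and SAP*

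**What the plan says.** Section 11.1.1 of the combined protocol and SAP sets the endpoint: "The primary endpoint is the pathologic response rate". On its analysis, section 11.2 says "Descriptive statistical analysis will be conducted for the primary and secondary endpoints" and then "The proportion with 95% confidence interval will be summarized for the categorical variables". That subsection gives no test, no success cut-off and no method for the interval.

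Section 11.3 follows directly: "This is a single-stage single-arm phase II clinical study". It continues: "We expect to enroll a total of 20 patient for achieving 80% power at a significance level of 5% using one-sided binomial test". On the hypotheses it says "The null hypothesis to be tested is that the pathologic response rate is 25" per cent, and that the rate assumed with the study regimen "for high risk soft tissue sarcomas is at least 52" per cent. It states no number of responders for rejection and does not refer back to the interval in 11.2.

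**The concern.** A reader who opens only section 11.2 finds a primary analysis with no hypothesis test. The one formal-looking quantity is a 95% interval, and the natural temptation is to call the trial positive when that interval lies above 25%. That is a stricter rule than the one-sided 5% test used for the sample size. At the smallest rejecting result the report could show a one-sided p-value of 0.041 beside an interval that still contains the null.

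If the interval then settled the matter, one more responder would be needed and the trial would have about 66% power instead of the 80% it was sized for. Because the interval method is not named, the reading of a borderline result could also depend on a choice made after the data were seen.

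**Working it through.** **Inputs.** From section 11.3: n = 20, null rate p0 = 0.25, target rate p1 = 0.52, one-sided level 0.05, binomial test. From section 11.2: a 95% interval, method not stated. X is the number of responders.

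**1. Reproduce the plan's power.** The cut-off is the smallest r with P(X ≥ r | 20, 0.25) ≤ 0.05.

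| r | P(X ≥ r), p = 0.25 | P(X ≥ r), p = 0.52 |
|---|---|---|
| 8 | 0.1018 | 0.9031 |
| 9 | 0.0409 | 0.8023 |
| 10 | 0.0139 | 0.6568 |

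The value 0.1018 exceeds 0.05 and 0.0409 does not, so r = 9. The attained level is 4.1% and the power 80.2%, which reproduces the stated 80%. The cut-off is not printed in the plan, but it follows uniquely from what is.

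**2. Set the 95% interval beside the test at 9/20 (45%).**

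- *Exact (Clopper-Pearson).* The lower limit solves P(X ≥ 9 | p) = 0.025. At p = 0.25 this tail is 0.0409, above 0.025, so 25% lies inside. The interval is 23.1% to 68.5%.
- *Wald.* 0.45 ± 1.96 × √(0.45 × 0.55 / 20) = 0.45 ± 0.218, which is 23.2% to 66.8%; 25% lies inside.
- *Mid-P.* Lower limit 24.6%; 25% lies inside.
- *Wilson.* 25.8% to 65.8%; 25% lies outside.
- *Agresti-Coull.* 25.8% to 65.8%; 25% lies outside.
- *Jeffreys.* 25.1% to 66.2%; 25% lies outside.

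Three of the six methods disagree with the test at 9/20 and three agree.

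**3. Neighbouring results.** At 10/20 all six methods exclude 25% (exact: 27.2% to 72.8%), in agreement with the test. At 8/20 the test does not reject, and no 95% lower limit reaches 25% (the highest is Wilson's, 21.9%). Of the 21 possible results, only 9/20 can produce a conflict.

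**4. Size of the conflict if the interval were the rule.** With exact, Wald or mid-P limits the cut-off becomes 10: level 1.4%, power 65.7%. The loss is 0.8023 − 0.6568 = 0.1455. This is also P(X = 9 | 0.52), the chance of landing on the disputed result, so the two describe one quantity and should not be counted as separate harms. With Wilson, Agresti-Coull or Jeffreys limits the cut-off stays at 9 and power at 80.2%.

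**5. The interval that matches the test.** The exact two-sided 90% interval puts 5% in the lower tail. At 9/20 it is 25.9% to 65.3% and excludes 25%. The gap in step 2 for the exact method is therefore the expected difference between 2.5% and 5% in one tail, and not a fault in the test or the sample size.

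**6. Which rule does the plan state?** Section 11.3 speaks of a null hypothesis to be tested and names the test and its level. The interval sentence in 11.2 covers categorical variables in general, which include wound complications as well as pathologic response. No sentence says that the interval must exclude 25% for success.

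**The case for a change.** The strongest case for acting is that section 11.2 is the analysis plan, calls the primary analysis descriptive, and never points to the test. In a 20-patient trial one responder can turn the result, so the rule should be plain in advance. The conflict is also realistic. The exact interval is the natural companion of an exact test. For the group's earlier 25-patient study, section 2.4 reports 40% with limits of 21% and 59%, and among the methods tried the Wald interval on 10/25 (20.8% to 59.2%) is the one that matches both. Both of these methods include 25% at 9/20. At a true rate of 52%, that result would occur in about one trial in seven.

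What stands is that 11.2 does not cross-refer to 11.3, that the interval method is open, and that a report of 9/20 could carry a significant one-sided p-value beside a 95% interval containing the null. What does not stand is that the plan therefore lacks a test or delivers 66% power. The two subsections are adjacent parts of one statistical chapter and are meant to be read together. The lower power needs a success rule that neither contains, together with particular interval methods. A two-sided 95% interval reported beside a one-sided 5% test is common practice: the test answers the hypothesis and the interval shows precision.

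**Conclusion.** No change is needed. This is a gap that analysts fill sensibly. Read together, sections 11.2 and 11.3 give a one-sided 5% binomial test of 25%, rejecting at 9 or more of 20 with a 4.1% error rate and 80.2% power at 52%, accompanied by a descriptive 95% interval. Followed that way, the plan reaches a sound conclusion at every possible result.

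The fall to 65.7% power is conditional: success would have to be judged by an exact, Wald or mid-P two-sided 95% interval, which the plan does not ask for. Even then only 9/20 is affected. A cross-reference in 11.2 or an added 90% interval would tidy the presentation, but would alter neither the test, the sample size nor the conclusion.

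This rests on three assumptions: exactly 20 patients are analysed, the binomial test in 11.3 is computed exactly (which reproduces the stated power), and the hypothesis is judged by that test.

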2.2 Adjuvant Radiotherapy

The ability to perform limb-salvage surgery was facilitated by the introduction of adjunctive radiotherapy. Adjuvant radiotherapy for soft-tissue sarcoma was initially described by Suit and Lindberg, who demonstrated improved local control rates of extremity sarcomas in over 80% of patients.^{1,2,5} Preservation of function of the limb was achieved in greater than 90% of cases. Randomized trials have validated the efficacy of the limb-sparing approach in achieving excellent local control rates that have eliminated the need for amputation for the majority of patients. A prospective, randomized clinical trial of limb-sparing surgery plus radiation versus amputation found equivalent recurrence-free survival rates.⁶ A randomized study of limb-sparing surgery plus or minus adjuvant radiation showed a significant decrease in local recurrence in those patients receiving radiation.³ Radiotherapy has clearly demonstrated its utility in improving local control rates and reducing the amputation rate.

Administration of radiation can be performed either pre- or postoperatively. A randomized study showed an increased acute wound complication rate with preoperative radiation compared to postoperative radiation.⁷ However, longer follow-up has suggested that postoperative radiation is associated with a greater incidence of long-term complications, such as subcutaneous fibrosis, that tend to be permanent problems and are probably due to the larger field size and higher radiation dose that

are used with postoperative treatment.⁸ In terms of efficacy, local control rates are the same whether the radiation is administered pre- or postoperatively.⁷ The use of pre- vs. postoperative radiation varies between institutions and is a matter of preference of the surgeon and radiation oncologist. Preoperative administration has been the preference at our institution. Theoretical advantages of preoperative radiation include delivery to undisturbed, well-oxygenated tissue. The field size does not need to be increased as it does in post-operative radiotherapy, allowing for lower radiation doses.⁹ Importantly, pathologic examination of the tumor specimen after surgery for necrosis allows assessment of the efficacy of the pre-operative treatment that may correlate with overall survival.¹⁰

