8.6 Follow-up

Follow-up for all patients registered on this study, including those who do not receive any protocol therapy, will be required until the patient's death. Follow-up after completion of protocol therapy will be limited to monitoring for 1) development of local tumor recurrence, 2) development of distant metastatic disease, 3) survival, and 4) late toxicity, including limb function impairment and secondary malignancy. Follow-up reports are due every 4 months.

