8.7 Schedule of Events

	Prior to Registration	Prior to Day 1 of each cycle*	Time of Pre-Surgical Restaging**	Post Treatment Follow-up
Tests & Observations				
History and Progress Notes	X	X	X	X
Physical Examination	X	X	X	X
Pulse, Blood Pressure###	X	X	X	X
Height/Weight***	X	X		
Performance Status	X	X	X	X
Treatment Toxicity Assessment		F	F	F
Pathology Review	A		A	
Laboratory Studies				
CBC, Differential, Platelets	X	B,C	X	PRN
Serum Chemistries#	X	B,C	X	PRN
Urinalysis	X	C		
Pregnancy Test##	X	X		
INR	X	H		
EKG	X			PRN
MUGA or ECHO	X		X	D
Blood for correlative studies (Section 7.1)	X	X	X	
Staging				
Chest CT	X		X	E
MRI or CT of primary site	G		G	E

* To be performed within 1 week of each chemotherapy cycle

** After completion of cycle 3 of chemoradiotherapy and within 4 weeks of surgery

*** Height only needs to be checked prior to cycle #1 if the patient's height is stable (i.e. not currently in puberty).

Electrolytes (including Phos, Mg), BUN, creatinine, bilirubin, AST, ALT, alkaline phosphatase

For women of childbearing potential. Screening pregnancy test does not need to be repeated if within 7 days of start of Sorafenib run-in. Will be repeated prior to each cycle of chemotherapy.

Blood pressure to be monitored weekly during the first 6 weeks of protocol treatment

A Initial diagnostic pathology specimen as well as post-operative specimen must be submitted for central review. Both specimens may be submitted together after surgery

B To be checked once weekly during each cycle or as clinically indicated

C Must be checked within 24 hours prior to each chemotherapy cycle

D As clinically indicated

E Post-treatment imaging studies for disease recurrence is at investigator's discretion. It is suggested that a chest CT or chest X-ray be performed every 4 months for the first 2 years, every 6 months for the 3rd year, and yearly for the 4th and 5th year. It is suggested that MRI or CT of the primary site be obtained yearly for the first 3 years.

F Toxicity assessments per CTCAE v 4.0 (See section 8.3). Long term follow-up for radiation toxicity and limb function required per section 8.3

G An MRI or CT of the primary tumor should be performed within 6 weeks prior to registration and again prior to surgery per standard care decision of the subject's surgeon

H INR should be closely monitored for patients receiving warfarin. INR does not need to be monitored during study for patients not receiving warfarin.

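### Late radiation and limb toxicity is followed until death, but the analysis section offers only a proportion with no time point, so the reported rate would depend on the data cut

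*Combined protocol and SAP*

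**What the plan says.** Late toxicity is a required outcome. Section 8.3 has acute and long-term radiation toxicity assessed by CTCAE category: radiation dermatitis, fibrosis, and events relevant to limb function. Section 8.6 lists among the follow-up items "4) late toxicity, including limb function impairment and secondary malignancy", with follow-up until death and reports every 4 months. Footnote F of section 8.7 adds: "Long term follow-up for radiation toxicity and limb function required per section 8.3".

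Safety is the first secondary objective (section 1), and level of toxicity is a secondary endpoint (section 11.1.2).

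Section 11.2 treats primary and secondary endpoints descriptively, with two tools. One is Kaplan-Meier for the survival functions. The other is: "The proportion with 95% confidence interval will be summarized for the categorical variables". The time-to-event measures in section 9.5 cover recurrence, disease-free, progression-free and overall survival; none is a toxicity measure. Section 11.4 expects accrual of 1 patient per month over 20 months. For late toxicity there is no landmark time, minimum follow-up, denominator, censoring rule or data cut.

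**The concern.** A proportion suits an outcome observed once per patient at a fixed moment, such as necrosis in the resected specimen. Late toxicity accrues over time, and these patients will have been watched for very different lengths of time when the data are cut. Events divided by patients counts someone with a few months of follow-up as free of late toxicity, and the binomial interval treats that as a complete observation.

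The result would be a late-harm rate with no time attached. It could not be set beside the 2-year survival figures that section 2.4 reports for the earlier regimen, and an early cut would tend to make it too low.

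**Working it through.** **The plan's own figure.** Section 11.3 plans 20 patients for 80% power at one-sided 5%, 25% against 52%. The exact binomial rule of at least 9 responses in 20 gives alpha 0.041 and power 0.802, so the figure reproduces. This point does not touch it. The documents state no figure for late toxicity.

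**Inputs from the documents.** Accrual is over 20 months (11.4). Surgery is at about day 78 (section 4), which is 78/30.4 = 2.57 months after entry. Two-year survival with the earlier regimen was 84% (2.4).

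**Assumptions.** Entry is uniform. Hazards are constant from surgery, and the 84% is applied from surgery. The denominator is all patients, each with surgery at day 78. The true 24-month cumulative incidence of late toxicity, with death competing, is 20%, 30% or 40%.

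**Step 1: follow-up from surgery.** For a cut c months after last entry, it runs from c − 2.57 to c + 17.43 months.

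| Cut after last entry | Follow-up from surgery (months) | Under 12 months | 24 months or more |
|---|---|---|---|
| 6 | 3.4 to 23.4 | 43% | 0% |
| 12 | 9.4 to 29.4 | 13% | 27% |
| 18 | 15.4 to 35.4 | 0% | 57% |
| 24 | 21.4 to 41.4 | 0% | 87% |

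**Step 2: hazards.** The death hazard is d = −ln(0.84)/24 = 0.00726 per month. With toxicity hazard h and s = h + d, cumulative incidence at time t is (h/s)(1 − e^(−st)). Setting this to 0.30 at 24 months gives h = 0.01638, s = 0.02365 and h/s = 0.693.

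**Step 3: expected crude proportion.** This is the cumulative incidence averaged over follow-up from a = c − 2.57 to a + 20, which is (h/s)[1 − (e^(−sa) − e^(−s(a+20)))/(20s)]. For c = 6, a = 3.43, and the result is 0.693 × [1 − (0.922 − 0.575)/0.473] = 0.184. In full:

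| True 24-month incidence | Cut +6 | +12 | +18 | +24 |
|---|---|---|---|---|
| 20% | 12.0% | 16.6% | 20.8% | 24.5% |
| 30% | 18.4% | 25.1% | 31.0% | 36.0% |
| 40% | 25.1% | 33.8% | 41.0% | 47.0% |

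In patients out of 20, the 30% row is 3.7, 5.0, 6.2 and 7.2 expected events.

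**Step 4: is it deaths or follow-up?** Set d = 0 and recalibrate to a true 30%. The crude figure then runs from 17.8% (+6) to 37.1% (+24), against 18.4% to 36.0% with deaths. The spread comes from length of follow-up.

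**Step 5: onset timing, 30% case, cuts +6, +12 and +24.** If toxicity arises only between 6 and 24 months after surgery, the crude figures are 14%, 22% and 30%. If it arises only in the first 12 months, they are 26%, 30% and 30%. The +6 cut understates in every scenario, most when toxicity is truly late. The excess at +24 needs events that continue beyond 24 months.

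**The case against.** The strongest reply is that section 11.2 never names late toxicity. The crude-proportion reading follows from its general rule, and all patients as denominator is an assumption. That is correct: the plan is silent here rather than committed to a poor method. But no other method in 11.2 fits graded toxicity, and the silence extends to time point, denominator and cut, so the gap stands.

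The size can also be questioned. The rate, the hazards and the cuts are assumed, and no section plans a cut 6 months after last entry. In the 30% case the +12 cut expects 5 events where the true rate implies 6 (20 × 0.30), a difference of one patient. The exact 95% interval for 5/20 is 8.7% to 49.1%. At +18 the crude figure is close to the 24-month target. This limits the importance of the point; it does not supply a time point.

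A reader might infer that the plan is wrong because early deaths count as toxicity-free. The documents and the arithmetic do not support that. Removing deaths leaves the spread essentially unchanged (step 4). A competing-risk estimator also treats a patient who dies first as never having the event, and properly so at a fixed time. At 84% two-year survival, only 1 − 0.84^(6/24) = 4.3% would be dead by 6 months, about 1 of 20. Eligible stage IV patients could raise that, but the documents give no figure.

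A reader might also take the remark in section 2.2, "such as subcutaneous fibrosis, that tend to be permanent problems", as evidence of expected late harm from this regimen. In context it describes the greater long-term complication rate of postoperative radiation, and it forms part of the case for preoperative treatment. It does not support a rate here.

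**Conclusion.** The point holds as a reporting gap. Late toxicity is collected without a fixed horizon, and the only applicable rule yields a proportion with no time attached. With a true 24-month incidence of 30%, the expected crude rate would be anywhere from 18% to 36% for cuts 6 to 24 months after last entry, under constant hazards, uniform 20-month accrual, 84% two-year survival and an all-patient denominator. The 20% and 40% cases behave alike (12% to 25%, and 25% to 47%). The size depends on when toxicity appears.

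The mechanism is unequal follow-up. The consequence is confined to a descriptive secondary safety summary in 20 patients: no test or sample size depends on it, and intervals would be wide under any method. It is a worthwhile, inexpensive improvement and not a flaw in the design.

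**What to change.** In section 11.2, name late toxicity as a separate summary:

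- Report it as cumulative incidence from surgery by the Aalen-Johansen estimator, with death as a competing event and censoring at the last toxicity assessment.
- Give estimates at stated times such as 12 and 24 months, each with 95% CI and number at risk, plus median follow-up and the data-cut rule. With a cut 6 months after last entry nobody has reached 24 months, so the rule must let follow-up mature before that estimate is reported.
- The sponsor sets the grade threshold and the event list (fibrosis, limb-function events, secondary malignancy) in advance.
- Patients who never reach surgery have no start date on this clock and should be accounted for separately.
- Keep crude proportions for acute toxicity and wound complications.

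The cost is SAP wording and minor programming. Start and stop dates of adverse events are already recorded (10.6.6) and follow-up reports already come every 4 months, so no visit is added. The downside is wide intervals at 24 months with 20 patients.
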